### 1. Background and Significance

Hypertension is a major public health problem affecting an estimated of 100 million Americans and is projected to cost the healthcare system upwards of \$220 billion by 2035. Racial disparities in hypertension control have been recognized for decades. The prevalence of hypertension among black adults is substantially higher than in non-Hispanic white adults. Despite modest improvements in treatment initiation, control rates in black patients continue to lag. These disparities are especially problematic because of racial differences in the consequences of disease. For example, a 10-mmHg difference in systolic blood pressure is associated with an 8% increase in stroke risk for whites but a 24% increase for blacks. Rates of hypertension treatment and control are more than 10% lower for Hispanic/Latinos than whites. Hispanics/Latinos also experience worse long-term cardiovascular health outcomes, with higher risks of stroke and end-stage renal disease than whites.

There are many contributors for the persistent racial/ethnic differences in hypertension control outcomes. [name], Advocate co-investigator, conducted a widely-cited systematic review of barriers to hypertension control and proposed a conceptual framework. Of these, a lack of treatment intensification, underuse or prescribing of racially-based oral antihypertensives, and suboptimal follow-up care are thought to be central contributors to racial/ethnic disparities.

In up to half of treatment episodes, healthcare providers do not intensity antihypertensive treatment when indicated, often referred to as clinician inertia. [name] systematic review identifies several contributors including clinicians being inappropriately satisfied with their patient's current level of control, concerns about treatment side effects, and concerns about accuracy of blood pressure readings obtained during office visits. Clinical inertia may pose a greater problem for minorities. The 2014 JNC-8 guidelines and the 2018 ACC/AHA antihypertensive guidelines now explicitly recommend specific treatment choices for hypertension based on race/ethnicity. Some clinicians remain unaware of the nuances in guidelines, and non-guideline concordant antihypertensive treatment, for black patients in particular, may still contribute to differences in blood pressure control between groups.

Effectively managing hypertension also relies on the ability to monitor response to therapy. Despite guideline recommendations for close follow-up when adjusting drug regimens, minority patients are less likely to return to clinical care than white patients. Patient self-management, such as blood pressure

monitoring necessary for titration, are also lower among minority patients, in part because of inability to afford in-home blood pressure monitoring cuffs as well as differential recommendations by providers about self-monitoring. Other social determinants of health, such as poor health literacy and limited insurance coverage, are more prevalent among black and Hispanic/Latino patients. Referral rates to social work and nephrologists for renal care are also lower, which further increases gaps in health outcomes.

Many EHRs systems contain a range of clinical decision support tools such as alerts, reminders, and defaults. The widespread adoption of EHRs presents a scalable opportunity for the implementation of EHR-based interventions. The existing literature supports the potential for health information technology (IT) to improve health care quality. In a recent systematic review, 56% of 236 studies found that decision support improved prescribing and preventive care. Of 147 studies that evaluated clinical outcomes, >75% showed that EHR tools improved these outcomes. Despite this encouraging evidence, few studies have evaluated how health IT can be leveraged to reduce disparities, particularly as other research suggests that the adoption of patient-facing tools, such as EHR portals, is up to 50% lower in minority patients.

Despite the promise of EHR-based interventions to improve health care quality, to our knowledge, only two trials have specifically sought to prospectively evaluate whether EHR-based interventions can reduce racial/ethnic disparities. One of these demonstrated that EHR-based “report cards” provided to physicians could reduce disparities in diabetes care. The other trial found that guideline-based decision support reduced disparities in hypertension treatment. Other observational studies have also provided supportive evidence. Across these studies, performance reports, decision support, and registries appear to be the most successful strategies.

**Therefore, we propose a pragmatic randomized trial to test the impact of a multicomponent health IT intervention on blood pressure control and racial and ethnic disparities.**

## 2. Specific Aims and Objectives

The overall goal of this project is to improve existing decision support for hypertension control and to reduce disparities in treatment, consistent with professional guidelines and quality metrics. To achieve this, we will **conduct and evaluate a cluster randomized trial to determine whether health IT tools targeted to providers improve blood pressure control for patients with uncontrolled hypertension.**

Our primary hypothesis is that a health IT intervention will improve systolic blood pressure (primary outcome), concordance with hypertension guidelines (secondary outcome), diastolic blood pressure (secondary outcome), treatment intensification (secondary outcome), and post-visit patient-provider follow-up (tertiary outcome) compared with usual care.

The objectives and endpoints are summarize below:

OBJECTIVES	ENDPOINTS	JUSTIFICATION FOR ENDPOINTS
Primary		
To determine whether multicomponent EHR-based health IT tools designed using behavioral	Change in systolic blood pressure from identification to 12-month follow-up, using values in the EHR	These outcomes are rapidly measurable using EHR data and will provide evidence of blood pressure control.

Mass General Brigham Institutional Review Board  
Intervention/Interaction Detailed Protocol

OBJECTIVES	ENDPOINTS	JUSTIFICATION FOR ENDPOINTS
principles targeted at providers improve blood pressure control for patients with uncontrolled hypertension as compared with usual care (no intervention).		
Secondary		
To determine whether multicomponent EHR-based health IT tools designed using behavioral principles targeted at providers improve concordance with hypertension guidelines, diastolic blood pressure control, and treatment intensification compared with usual care.	
Percentage of patients with well-controlled blood pressure (<140/88mmHg) at 24 months follow-up, using values in the EHR.
 
Percentage of patients with intensification of medication in the 24-month follow-up period, defined by addition of therapy or increasing dose.
 
Percentage of patients with guideline-concordant medications ordered in the follow-up period.
 
Change in the gap in systolic blood pressure between Black and Hispanic/Latino patients and non-Hispanic patients from identification to 12-month follow-up
 
Change in diastolic blood pressure from identification to 12-month follow-up
	These outcomes capture the extent to which there is an improvement in concordance with hypertension guidelines, diastolic blood pressure control, and treatment intensification during the follow-up period.
Exploratory		
To better understand patient and provider's perspective on hypertension management through the AAH healthcare system	Analysis of de-identified qualitative interviews including patients and providers from AAH primary care sites	These outcomes will inform the research methods and health IT tool design for the pragmatic cluster randomized trial.
To determine whether multicomponent EHR-based health IT tools designed using behavioral principles targeted at providers improve post-visit patient-provider follow-up compared with usual care.	Clinical encounters, using number of office visits, telephone calls and patient portal interactions between AAH primary care providers and patients during the 24-month follow-up period	These outcomes measure the post-visit patient-provider follow-up during the follow-up period.
To assess the implementation of the intervention in practices	Adoption of the EHR interventions and integration of the intervention into clinics	These outcomes will be used to evaluate aspects of the implementation of the intervention and will provide valuable information regardless of the clinical results of the trial.

### 3. General Description of Study Design

#### 3.1 Study site

[figure not shown]
The study will be conducted in outpatient primary care practices of Advocate Aurora Health (AAH), a large integrated delivery network in Wisconsin and Illinois. AAH has a fully functional EHR, Epic, that supports computerized ordering of medication.

#### 3.2 Overall design

**In the first Phase (Aim 1),** we will analyze 30 de-identified qualitative interview transcripts that were conducted with 15 patients and 15 providers (14 primary care physicians and 1 medical assistant) from two AAH primary care clinics to understand perspectives on hypertension management and identify opportunities to improve EHR tools for providers. The interviews were previously conducted between October 2020 and March 2021 under the oversight and approval of the Advocate Aurora Health IRB. In brief, treating physicians provided approval for potential patient participants to be contacted. Eligibility criteria for the interviews included a diagnosis of hypertension and seeking care at one of the two pilot practices. After approval, patients were contacted for their willingness to be interviewed and consent was obtained using a fact sheet. Providers were eligible for the interviews based on their practicing as clinicians in the pilot practices. Each interview was conducted using an approved semi-structured interview guide and were audio-recorded and subsequently transcribed. Participants were offered compensation for their time. All data were previously de-identified. We are seeking approval by the MGB IRB for the analysis of the de-identified data collected during these interviews.

**In the second Phase,** we will conduct a 2-arm pragmatic cluster randomized clinical trial to evaluate whether a multicomponent health IT intervention improves blood pressure control and reduces racial/ethnic disparities. Participating clinics will be randomly assigned to one of 2 arms: (a) Arm 1: multicomponent, intervention and (b) Arm 2: usual care (i.e. no intervention). Providers and in each arm will receive the same intervention for up to 24 months after randomization, which will allow us to determine the relative effectiveness of each approach as well as their long-term impact on clinical outcomes. Primary care providers in the intervention clinics will receive electronic decision support tools to guide their care of eligible patients. Providers in usual care clinics will receive usual care at AAH. Patients will not receive any intervention or outreach independent of their provider or care team. We will use EHR data to implement the EHR tools, identify study subjects, track study progress, and evaluate the effect of the interventions.

#### 3.3 Study schema

## 4. Subject Selection

### 4.1 Inclusion Criteria

The trial will include provider subjects with eligible patients. Specific decision support at the point of care will also appear for patients whose latest outpatient/ambulatory blood pressures are elevated (i.e.,  $SBP \geq 140$  or  $DBP \geq 90$ ). There is no upper limit for SBP or DBP, as this cutpoint is driven by HEDIS criteria and would otherwise exclude patients who may be in greatest need of care. Limited inclusion criteria will be applied to maximize generalizability in accordance with pragmatic trial principles outlined by PRECIS-2 (Pragmatic Explanatory Continuum Indicator Summary). The patient population will only be included for the purpose of providers receiving decision support and for the purpose of analyzing the effect of the intervention. The study criteria are defined below.

**Provider-subjects** will receive EHR interventions if they are primary care providers (internal medicine, family medicine, geriatrics) employed by AAH at one of the 24 participating clinics cluster randomized to the intervention.

**EHR patient data will be collected retrospectively** for analysis and used for the EHR tools for providers based on the following criteria:

1. Medical Group Medical Home Population: 1 visit with PCP in past 2 years (rolling 24 months) and Patient has a medical group PCP as their EPIC General PCP
2. Current age 18-85 years

3. Hypertension diagnosis on EPIC Problem list OR at least 2 visits (office/telehealth/telephonic) with an encounter diagnosis of HTN on different dates, with at least one during the last 24 months (rolling dates)
4. Latest outpatient/ambulatory (exclude urgent care) SBP  $\geq 140$  or DBP  $\geq 90$  (12 months rolling) (lowest measure if more than one taken at the same time) (no upper limit)

#### 4.2 Exclusion Criteria

Providers and patients not meeting the inclusion criteria above will not be included in the analysis of the trial. No other exclusion criteria will be used.

#### 4.3 Recruitment and Retention

##### *4.3.1 Inclusivity of study subjects*

The primary study population for receiving any of the EHR-based interventions will be primary care providers at one of the 24 clinics. Providers will receive EHR-based decision support tools for the care of their eligible patients. Eligible patients are those based on HEDIS quality improvement criteria used at AAH and will include those 18-85 years of age, having had 1 visit with their primary care provider in the last 2 years and are diagnosed with hypertension. Specific decision support at the point of care will also appear for patients whose latest outpatient/ambulatory blood pressures are elevated (i.e., SBP $\geq 140$  or DBP $\geq 90$ ). The patient population will only be included for the purpose of providers receiving decision support and for the purpose of analyzing the effect of the intervention.

Pilot data indicate that participants will cover a broad range of participants by gender and race/ethnicity. Of these, 39.8% are White, 37.4% are Black or African American, 7.3% are Hispanic, 5.0% are Asian/Pacific Islander, 9.7% are other races or unknown. Further, given the minimal risk nature of the study, participants will not receive incentives, remuneration, or be required to provide informed consent.

## **5. Subject Enrollment**

### 5.1 Waiver of informed consent

We are seeking a waiver of informed consent and HIPAA authorization for all data collected in this study, including the previously conducted deidentified patient interview transcripts. The goal of this project is to improve decision support to increase guideline concordant care for patients with poorly controlled hypertension. First, the nature of this intervention involves testing EHR decision support directly for providers (using information already available to them and a similar infrastructure they use in the course of regular clinical care). Second, the ability to understand the true effect of the intervention as it is delivered in the real world would be difficult to ascertain if true informed consent was sought. Third, obtaining informed consent would predictably reduce the number of patients participating in the study, especially those from unrepresented populations, and therefore undermine the generalizability of the study results, a foundational aspect of pragmatic clinical trial principles. Fourth, providers will retain all oversight of their patients' care and will be able to make therapeutic choices based using their professional judgement. Fourth, this approach has also been approved by Advocate clinical leadership and their IRB. We also request a HIPAA waiver of patient authorization to access EHR data (retrospectively) necessary for outcome evaluation, as doing so would be impractical and infeasible to conduct the study.

An organization-wide announcement will be circulated across participating AAH clinics to inform providers of the launch of an intervention leveraging clinical decision support tools to support improved prescribing for adults. Providers randomized to the intervention group will also receive basic quality improvement training on the EHR decision support tools, as is currently done at AAH in usual care.

### **5.2 Randomization and blinding**

Clinics will be randomized to treatment arms in equal proportions. We will use clinic-based cluster randomization to minimize the possibility of contamination in study interventions between practices and clinic staff. For the randomization, we will use covariate constrained randomization in R software based on clinic characteristics to reduce potential imbalances between the clinics assigned to the treatment arms. The clinics/providers will not be blinded to which arm they were assigned to, as blinding in the context of an intervention that is intended to motivate action will be infeasible. Physicians randomized to usual care will not have any way of accessing the EHR interventions. Patients of physicians in the usual care arm will have access to the patient portal but will not be receiving any assistance from medical assistants or any of the after-visit activities. Moreover, only primary care physicians will be included (specialists will not receive any enhanced clinical decision support or report cards), and feasibility data suggest that there is minimal crossover of patients with other primary care physicians given the nature hypertension management at Advocate. Therefore, any risk of contamination within practices is low, and any contamination that does exist would bias the trial results towards the null.

## 6.2 Study interventions

Clinics randomized to the control arm will not receive any additional EHR-based tools outside of the current standard tools offered to Advocate providers and patients. The intervention arm will receive EHR-based tools that will be delivered at several time points during a patient's care episode.

### 6.2.1 Provider Training

Prior to study implementation, providers randomized to the intervention arm will receive a brief quality improvement training on how to use the new EHR-based tools. Providers will not be required to use these tools for the purpose of this study but will be offered these training opportunities to ensure they can properly utilize them if they choose to do so, as is standard AAH practice for implementing new EHR tools.

### 6.2.2 Pre-visit interventions

Providers in the intervention arm will receive an EHR-embedded dashboard which will highlight racial/ethnic differences in rates of achieving blood pressure control within their patient panel. Using EHR data, we will identify eligible patients: (1) Medical Group Medical Home Population: 1 visit with PCP in past 2 years (rolling 24 months) and Patient has a medical group PCP as their EPIC General PCP, (2) current age 18-85 years, (3) hypertension diagnosis on EPIC Problem list OR at least 2 visits (office/telehealth/telephonic) with an encounter diagnosis of HTN on different dates, with any during the last 24 months (rolling dates) performing provider, and (4) latest outpatient/ambulatory (exclude urgent care) SBP  $\geq$ 140 or DBP  $\geq$ 90 (12 months rolling) (lowest measure if more than one taken at the same time).

Among these eligible patients, patients included in the primary analysis will be those that had an in-person visit at one of the trial clinics. This is because the primary decision support aimed at providers is based on office visits. Patients are first identified as eligible for this analysis based on the first time that they had a visit at one of trial clinics. The dashboard will also provide individual-level information for patients with poorly-controlled blood pressure including (a) most recent blood pressure values, (b) current therapies (based on the medication list), (c) next scheduled appointment, and (d) social determinant needs. Patients in the intervention arm will receive outreach via MyChart, a component of the patient portal, to answer questions regarding their social determinants of health (SDoH).

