### **6.5 Study endpoints**

The trial will be completed 24 months after trial launch. At the end of the study period, data will be extracted retrospectively from electronic health records; the primary analysis will be on patients who visited one of the 24 clinics during the study period and who meet the inclusion criteria.

Primary:

- Change in systolic blood pressure from patient identification (i.e., the most recent encounter that identified the patient as eligible) through 12-month follow-up, using values recorded in the EHR

Secondary:

- Percentage of patients with well-controlled blood pressure (<140/88mmHg) or <130/80 mmHg for those with comorbid conditions defined by clinical guidelines at 12 months follow-up, using values in the EHR
- Percentage of patients with intensification of medication in the 12-month follow-up period, defined by addition of therapy or increasing dose
- Percentage of patients with guideline-concordant medications ordered in the 12-month follow-up period
- Change in the gap in systolic blood pressure between each of Black and Hispanic/Latino patients and non-Hispanic White patients from the last encounter before identification through 12 months after, using values in the EHR
- Change in diastolic blood pressure from the encounter before identification through 12 months after, using values recorded in the EHR

Exploratory:

- Frequency of viewing the dashboard, SmartSet order set, documentation choices, and acknowledgement reasons
- Intervention fidelity: BPAs (alerts) firing as intended

Clinical encounters, using number of office visits, telephone calls and patient portal interactions between AAH primary care providers and patients during the 12-month follow-up period. These outcomes will also be measured in the remainder of the follow-up period until the end of administrative censoring at the end of the 2-year trial.

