## **9. Statistical Analysis**

### 9.1. Statistical hypothesis

We hypothesize that the intervention will lower mean systolic blood pressure to a larger degree than usual care. The null hypothesis will be no difference between patients identified as eligible in the intervention arm and usual care. All analyses will use intention-to-treat principles.

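### The primary patient cohort forms after clinics are randomized, so entry could differ by arm, and the plan has no fixed-panel analysis or entry comparison to show whether it did

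*Combined protocol and SAP*

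**What the plan says.** Section 5.2 sets the unit of allocation: "Clinics will be randomized to treatment arms in equal proportions". The same section says clinics and providers know their arm.

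Patients join later. Under section 6.5, "the primary analysis will be on patients who visited one of the 24 clinics during the study period and who meet the inclusion criteria". Section 6.2.2 requires the visit to be in person: "patients included in the primary analysis will be those that had an in-person visit at one of the trial clinics". It explains that the main decision support works through office visits. Criterion 4 in section 4.1 requires the latest outpatient reading on a rolling 12-month window to be at least 140 systolic or 90 diastolic, using the "lowest measure if more than one taken at the same time".

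The index date is described in different ways. Section 6.2.2 says "Patients are first identified as eligible for this analysis based on the first time that they had a visit at one of trial clinics". The primary endpoint in section 6.5 starts from the most recent encounter that identified the patient. The power statement in section 9.2 counts from randomization.

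Section 9.1 says "All analyses will use intention-to-treat principles", and frames the null hypothesis in terms of the patients found eligible in each arm. The text available for review contains no analysis of a panel fixed before launch and no comparison of entry rates by arm.

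**The concern.** Randomization balances the clinics and the patients attached to them at that time. It does not by itself balance a subset that selects itself later, through attendance and a recorded reading, while the intervention is running. If intervention clinics see a different mix of their hypertensive patients, the two cohorts differ for reasons other than the effect on blood pressure.

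The outcome makes this matter more. It is a change from a baseline that must exceed a threshold, so part of every patient's fall is regression to the mean. If one arm's entrants regress more than the other's, the gap looks like a treatment effect or hides one.

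With no entry comparison and no fixed-panel analysis, a reader of the results could not separate selection from effect.

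**Working it through.** **1. The plan's own precision and power.** Inputs from section 9.2: 24 clinics, 49,395 patients, SD 13.5, ICC 0.1, difference 5.0 mmHg, alpha 0.05 (two-sided assumed; the plan does not say).

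- Mean cluster size: 49,395 / 24 = 2,058.1
- Design effect: 1 + (2,058.1 − 1) × 0.1 = 206.7
- Effective n per arm: 24,697.5 / 206.7 = 119.5
- SE: 13.5 × √(2 / 119.5) = 1.747 mmHg
- Power, normal approximation: 81.7%, which agrees with the stated figure of more than 80%. A t test on 22 df gives 78.1%.

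**2. Which components could act on entry.** The setting is a first-visit index, as in section 6.2.2.

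- *Dashboard (6.2.2).* It is available before visits and lists poorly controlled patients with their next appointment. This is the most credible route, although no section says it is used to recall patients and section 6.2.1 makes tool use voluntary.
- *Provider behaviour at unblinded, trained clinics (5.2, 6.2.1).* Possible, but weaker.
- *Patient portal.* "Patients in the intervention arm will receive outreach via MyChart", but its stated purpose is to collect answers on social needs. Weak.
- *In-visit alert (6.2.3).* It appears once the patient has presented, so it cannot cause that visit. No section says it prompts a repeat reading. Weak.
- *Nurse blood pressure checks (6.2.4).* These are post-visit, so they follow entry. Weak.

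If the index is instead the latest of several qualifying encounters, which the section 6.5 wording allows, the baseline reading can itself follow exposure and the last two routes become relevant.

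**3. Illustrative bias from extra entrants, with no true effect.** Suppose intervention clinics bring in an extra fraction x of patients whose 12-month change differs by g mmHg. Then bias = x / (1 + x) × g. Both inputs are assumed. Rejection is two-sided at SE 1.747.

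| x | g (mmHg) | Bias (mmHg) | Rejection under the null |
|---|---|---|---|
| 5% | 2 | 0.10 | 5.0% |
| 5% | 5 | 0.24 | 5.2% |
| 10% | 5 | 0.45 | 5.8% |
| 20% | 5 | 0.83 | 7.6% |
| 20% | 10 | 1.67 | 15.9% |

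For scale, if extra entrants have index SBP higher by e and the correlation with follow-up is r, regression to the mean alone gives g = e × (1 − r). With e of 5 to 10 and r of 0.4 to 0.6, g runs from 5 × 0.4 = 2 to 10 × 0.6 = 6. The last row is therefore an outer case.

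**4. The direction is not fixed.** A simulation with no treatment effect assumed usual SBP with mean 138 and SD 14, visit SD 8, reading SD 6, and the systolic rule only. With one reading, 45.4% qualify and mean change is −5.08 mmHg. If a second reading is taken in 10%, 25% or 50% of patients and the lower one counts, the share qualifying falls to 44.6%, 43.4% or 41.5%. Mean change becomes −4.81, −4.41 or −3.64. That is a shift of 0.27, 0.67 or 1.44 mmHg against the arm that rechecks more. Extra entry of higher-pressure patients pushes the other way. The recheck rates are assumptions with no basis in the documents.

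**5. What planned adjustment would catch.** Section 9.3 repeats analyses with adjustment where a standardized difference exceeds 0.1. Taking 13.5 as a proxy for the baseline SD, that is 1.35 mmHg. An imbalance just below the trigger leaves 1.35 × (1 − r) = 0.54 to 0.81 mmHg for r of 0.6 to 0.4.

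**6. Power of a fixed-panel analysis.** Suppose a share v of the panel visits and non-visitors have no effect. The panel is then 49,395 / v and the effect 5.0 × v. The SE stays near 1.746, because the number of clinics and the ICC set it.

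- v = 0.90: effect 4.5 mmHg, power 73.1% (69.3% by t test)
- v = 0.80: effect 4.0 mmHg, power 63.0% (59.1% by t test)

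**The case against.** The case for leaving the plan alone is substantial. Clinics keep their assigned arm, entry rules are the same in both arms, section 5.2 reports minimal patient crossover, and section 9.1 defines the comparison on eligible patients. Section 6.2.2 gives a sensible reason for requiring a visit. Several intervention components cannot plausibly bring a patient in. Section 9.3 provides for adjustment, including in the primary analysis when strong predictors are unbalanced, and a baseline SBP imbalance is measured and adjustable. A fixed panel has its own weakness: there are no study visits (section 6.3), so patients who never return have no 12-month value.

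Most of this stands, and it rules out stronger readings. A reader might infer that the trial is not intention-to-treat. The documents do not support that at clinic level. A reader might infer that every tool listed in section 6.2 recruits patients into the cohort. The stated purposes and timing do not support that either. It is also tempting to re-date the qualifying reading in criterion 4 for the primary analysis. That would change who is in the primary cohort, which is a trade-off the sponsor need not make to resolve this point.

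What the objection does not answer is that entry is unobserved by arm. Adjustment covers measured covariates only, and multiple imputation concerns outcomes of patients already included, not those who never enter.

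**Conclusion.** The point holds in a limited form. The primary cohort is assembled after randomization, under unblinded assignment, by a visit and a rolling reading, and the plan has no means of showing whether assembly differed by arm. The credible route is the dashboard, with provider behaviour second.

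Bias is possible, not shown. The documents give no entry rates, so its size and direction are unknown. The illustrative range of about 0.1 to 1.7 mmHg lies below one design SE (1.75), and for x up to 10% with g up to 5 it is under 0.5 mmHg. A reader might take the upper figure as an expected distortion; it rests wholly on assumed inputs. The conflict over the index date affects severity: a baseline taken at the latest qualifying encounter could follow exposure, which is a more serious problem than selective first visits.

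**What to change.** Keep the visit-based primary analysis and its criteria. In sections 6.5 and 9.3:

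- **(a)** Pre-specify a companion analysis of the primary outcome. Apply criteria 1 to 4 to data dated before launch, assign each patient to the clinic of their primary care provider at randomization, and include the patient whether or not a visit follows. Adjust for pre-launch SBP, and handle missing 12-month values with the multiple imputation and sensitivity analyses of section 9.3.
- **(b)** Report by arm the share of that launch-date panel that entered the visit-based cohort, with pre-launch SBP.
- **(c)** Reconcile the index date between sections 6.2.2 and 6.5, and align the time origin in section 9.2.
- **(d)** Describe the visit-based analysis as patients seen, analysed in their clinic's assigned arm.

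The cost is SAP wording and one more analysis from the same EHR source. Pre-randomization SBP is already scheduled in section 6.3, but the sponsor should confirm that the extract will cover panel patients who do not visit. The companion estimate is diluted by unexposed patients, at the power shown above, and has more missing outcomes. It cannot replace the primary result.
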